6.1.6.3 Follow Up after Withdrawal from Study (Early Termination)

Any adverse event resulting in withdrawal of a participant will be followed up until resolution or until the adverse event is judged by the principal investigator or designee to have stabilized where possible.

At the time of withdrawal, provided the participant is willing, all the requested termination visit procedures will be performed according to the Time of Events Schedule (**Appendix A**).

The date and reason for withdrawal (early termination) from the study should be collected and reported to the Sponsor at the RU, the SMC, and the local IRBs.

A pregnant participant will not receive the study drugs. If pregnancy occurs after 3BNC117-LS and 10-1074-LS administration, the participant will be followed until the end of the study and until delivery, if delivery occurs after the study has ended. Approximately 2-4 weeks after delivery, the baby will be examined by a pediatrician to assess his/her health status. The outcome of the pregnancy and the health status of the baby will be reported to the Sponsor at the RU, the SMC, and the local IRBs.

6.2 Study Procedures

6.2.1 Consent Procedure

Prior to the initiation of any study related procedures, the potential participants will be given a copy of the most recent IRB stamped and approved informed consent to read. Additionally, the PI or study staff member who has been designated to consent will discuss the specifics of the study including but not limited to the purpose of the research, procedures, time commitment, required tasks, test article, alternative treatments, benefits, risks, confidentiality, etc. in a comprehensible (non-scientific) manner, using language readily understandable by the participant. Participants will be told that participation is voluntary and that, if they do not consent, they will not be penalized. The person consenting will assure the voluntariness of the participant.

A private, confidential setting will be provided for the potential participant to read and discuss the informed consent free from coercion, undue influence or constraints of time. All participants will be given a chance to ask questions and express concerns. They will be given the option to take the consent home and discuss it with family, friends, and /or health care providers. After a participant and the person conducting the consenting process sign and date the consent, the participant will be given a copy of the signed informed consent form.

An enrollment note will be written in the source document as to who obtained consent, how, when, were questions asked and answered, and that a copy of the informed consent was given to the participant.

The "Teach Back" method will be used to ask research participants to repeat or "Teach Back" the information, concepts and directions that the staff member has attempted to convey to the participant. This method is used to assess comprehension and retention of protocol requirements, adverse event information, risks and benefits, and the participant's rights described in the Informed Consent process.

6.2.2 Study Assignment and Randomization

Enrollment will be open-label, and participants will be enrolled sequentially as they meet enrollment criteria. Study ID numbers will be assigned by the Emmes Corporation, to prevent over-enrollment. Over-enrollment will only be permitted to replace participants lost to follow up prior to week 4, as discussed in Section 8.2 Sample Size Considerations.

6.2.3 Study Drug Administration Procedure

3BNC117-LS will be provided in single-use vials containing 1 mL of the product at a concentration of 150 mg/mL. 10-1074-LS will be provided in single-use vials containing 1 mL of the product at a concentration of 140 mg/mL.

The volume of 3BNC117-LS to be administered will be calculated by the site research pharmacist. Weight measurements collected at the day 0 visit will be used to calculate the dose of 3BNC117-LS. The appropriate volume of 3BNC117-LS will be diluted in sterile normal saline to a total volume of 100 mL, and will be administered as an intravenous infusion over 30 minutes.

The volume of 10-1074-LS to be administered will be calculated by the site research pharmacist. Weight measurements collected at the day 0 visits will be used to calculate the dose of 10-1074-LS. The appropriate volume of 10-1074-LS will be diluted in sterile normal saline to a total volume of 100 mL, and will be administered as an intravenous infusion over 30 minutes, after the infusion of 3BNC117-LS is completed.

The study drugs will be administered via a peripheral vein in one of the upper extremities. The administration site should be free of potentially complicating dermatologic conditions. The entire contents of the infusion bags must be administered. At the end of each infusion, the IV line will be flushed with Normal Saline to ensure all the study drug has been delivered.

6.2.4 Medical History and Physical Examination

At the time of screening, participant's past medical history will be collected and will include details of any previous reaction to vaccination, and contraceptive practices. Interim medical histories will be collected at time-points according to the Time of Events Schedule (**Appendix A**).

A general physical examination will be conducted at screen including weight, height, vital signs, and examination of skin, respiratory, cardiovascular and abdominal systems. At the study drug administration and follow up visits, directed physical examinations will be performed according to the Time of Events Schedule (**Appendix A**). A directed physical examination will include vital signs, examination of infusion site, and any further examination indicated by history or observation.

Any participant with a grade 3 or 4 elevation in total bilirubin will undergo a diagnostic work up that includes right upper quadrant ultrasound, testing for gamma glutamyl transferase (GGT) HAV (IgM and IgG), HBV (hepatitis B surface antigen and IgM anti-hepatitis B core antigen), HCV (anti-hepatitis C antibody and HCV PCR), EBV (IgM and IgG VCA and EBNA antibodies), CMV (IgM and IgG), VZV (IgM and IgG) and HSV (IgM and IgG), and any other relevant laboratory tests as determined by the investigators. These evaluations will be of no cost to the participant.

6.2.7 Monitoring for Cytokine Release Associated Adverse Events and Treatment of Cytokine Release Syndrome, Immediate Hypersensitivity Reactions or Other

Life-Threatening Adverse Events

Based on previous clinical experience with similar monoclonal antibodies, it is unlikely that administration of 3BNC117-LS and 10-1074-LS would lead to cytokine release syndrome. However, a potential side effect of a monoclonal antibody can be the stimulation of a massive release of cellular cytokines, which can have profound effects on blood pressure, vascular integrity, and myocardial, lung, liver, and kidney functions. If cytokine release syndrome occurs, the participant may need to be treated with intravenous fluids, vasopressors, and high-dose corticosteroids and may require ventilator support.

Study participants will be observed at the site infusion unit on the day of study drug administration. 3BNC117-LS and 10-1074-LS will each be administered over 30 minutes. Participants will remain in the unit for at least 60 minutes after last infusion. Access to a twenty-four hour on-call physician is available at all sites. The study sites are equipped with crash carts for immediate medical care, should the need arise. In case of an emergency, after stabilization of the volunteer, he/she will be transferred to a tertiary care center for specialized medical care.

6.2.8 Family Planning Counseling

During screening and subsequent study visits, study personnel will counsel participants about the importance of prevention of pregnancies and the use of condoms, as well as other effective family planning methods. Condoms will be provided.

Female study participants of reproductive potential are defined as pre-menopausal women who have not had a sterilization procedure (e.g. hysterectomy, bilateral oophorectomy, tubal ligation or salpingectomy). Women are considered menopausal if they have not had a menses for at least 12 months and have a FSH of greater than 40 IU/L or if FSH testing is not available, they have had amenorrhea for 24 consecutive months.

Should pregnancy occur, a pregnant participant will not receive the study drug(s). If pregnancy occurs after study drug administration, the participant will be followed until the end of the study and until delivery, if it occurs after the study has ended. Approximately 2-4 weeks after delivery, a pediatrician will examine and assess the health status of the baby. The baby's health status will be reported to the Sponsor at the RU, the local IRBs, and the SMC.

6.2.9 Safety Assessments

6.2.9.1 Solicited Adverse Events

Solicited adverse events in this study include presence of feverishness, chills, headache, nausea, vomiting, malaise, myalgia and arthralgia occurring in the two weeks following 3BNC117-LS and 10-1074-LS administration, as well as infusion site reaction or extravasation changes.

Solicited adverse events will be collected prospectively by structured interviews on infusion and post-infusion follow up visits; recorded and graded according to pre-established criteria (see **Appendix B**). The DAIDS AE Grading Table, corrected v2.1 (July 2017) will be used to grade adverse events in HIV-infected participants. In addition, the Common Terminology Criteria for Adverse Events (CTCAE) v5.0 (27Nov2017) grading scale will be used for reporting and grading adverse events in all groups occurring within 24 hours of the start of 3BNC117-LS and 10-1074-LS infusions that are considered infusion reactions or cytokine release syndromes. Symptoms that may constitute an infusion reaction or cytokine release syndrome include: fever and/or shaking chills, flushing and/or pruritus, alterations in heart rate and blood pressure,

dyspnea or chest discomfort, back or abdominal pain, nausea, vomiting, and/or diarrhea, skin rash.

Vital signs (pulse, respiratory rate, blood pressure and temperature) will be measured prior to each antibody infusion, at the end, and 1-hour post-infusion, and will be graded according to the CTCAE v5.0 toxicity table and recorded. All medications required for treatment of adverse events will be recorded.

6.2.9.2 Unsolicited Adverse Events

During all follow up visits, the occurrence of unsolicited adverse events will be assessed following an open question to participants, with the dates of commencement and resolution and any medication required. Adverse events will be followed to resolution or stabilization. They will be graded as indicated in the appropriate toxicity table (**Appendix B**).

Laboratory abnormalities that are considered clinically significant and are grade 3 or higher will be reported as adverse events.

6.2.10 Blood Collection, Storage and Shipment

Venous blood will be collected at every study visit according to the Time of Events Schedule (**Appendix A**). Up to 120 mL will be collected at day 0. Up to 100 mL will be collected at other visits. At no time will the total volume of blood collected exceed 550 ml over an 8-week period. All specimens will be handled according to Processing Laboratory SOPs. Frozen PBMCs, plasma, and serum will be processed and stored at the study sites.

6.2.11 Routine Laboratory Parameters

Laboratory parameters will routinely include hematology (WBC and differential, hemoglobin/hematocrit, platelets), clinical chemistry (creatinine, total and direct bilirubin, AST and ALT, alkaline phosphatase), and urinalysis (dipstick). TSH, T3, and free T4 will be measured at week 0 and week 4. Female participants will have serum beta-HCG measured on the day of study drug administration, and urine beta-HCG checked at screening and follow up visits. The laboratory samples for these tests will be collected at the time points indicated in the Time of Events Schedule (**Appendix A**).

In the event of an abnormal laboratory value, participants may be asked to have additional sample(s) collected at the discretion of the principal investigator or designee.

HIV-1 viral load and CD4+ T cell counts will be closely monitored as outlined in the Time of Events Schedule (**Appendix A**).

Participants will be screened for syphilis (RPR), gonorrhea and chlamydia (urine GC/Chlamydia nucleic acid amplification test), and viral hepatitis (HBsAg and HCV viral load) at the Screening Visit.

6.2.12 Antiretroviral and Immunogenicity Assessments

1. Standard HIV-1 viral load assay (CLIA-certified). The detection range of the assay is 20-10x10⁶ copies/ml. HIV-1 viral load will be determined at multiple time points before and after 3BNC117-LS and 10-1074-LS administration.

2. Levels of circulating CD4+ and CD8+ T cell counts will be determined by a CLIA-certified assay.
3. Measurement of 3BNC117-LS and 10-1074-LS levels by sandwich ELISA will be performed in the laboratory of [name] at Duke University by qualified assays. mAb levels will be measured in serum at multiple time points during the study, according to the Time of Events Schedule (**Appendix A**).
4. Anti-drug (3BNC117-LS or 10-1074-LS) antibody responses in serum. Assays will be performed in the Laboratory of [name] at Dartmouth College by qualified assays, according to the Time of Events Schedule (**Appendix A**).
5. 3BNC117-LS and 10-1074-LS sensitivity (CLIA-certified). Baseline (day 0) sensitivity to 3BNC117-LS and 10-1074-LS will be evaluated by a PhenoSense assay developed by Monogram. In this assay, a library of pseudoviruses expressing envelope sequences isolated from PBMC proviral DNA is tested for neutralization sensitivity to a given bNAb in TZM.bl cells. Sensitivity will be defined as $IC_{50}s < 0.25 \mu\text{g/ml}$. This assay will be performed at Monogram.
6. Genotyping – Sequencing of HIV-1 env viral isolates will be performed in plasma samples collected before and after 3BNC117-LS and 10-1074-LS infusions. Genotyping will be performed in the RU Laboratory of Molecular Immunology.
7. Phenotyping of viral escape variants in viremic participants - HIV-1 pseudoviruses expressing selected envelope sequences will be generated for subsequent characterization by *in vitro* neutralization assays. Representative sequences, including sequences with substitutions not known to confer reduced susceptibility to 3BNC117 or 10-1074, will be selected for phenotypic analysis. Pseudoviruses will be generated in the RU Laboratory of Molecular Immunology and neutralization assays will be performed in the Laboratory of [name] at Beth Israel Deaconess Medical Center.
8. HLA-typing will be performed on PBMC samples at a contract laboratory.
9. Functional properties of cytotoxic T cells analysed by flow cytometry at baseline and following 3BNC117-LS and 10-1074-LS infusions. These assays will be performed in the RU Laboratory of Molecular Immunology.
10. TZM-bl neutralization assay will be performed in the laboratory of [name] of the Beth Israel Deaconess Hospital in Boston. This assay will be performed to determine serum neutralizing activity against a panel of pseudoviruses representative of multiple clades at baseline and following 3BNC117-LS and 10-1074-LS infusions.
11. Gene expression profile of isolated HIV-1 infected cells by single cell RNA sequencing will be performed in the RU Laboratory of Molecular Immunology.

Optimal sample collection, processing, cryopreservation, archiving and storage will be maintained. Additional studies will be performed as warranted at the discretion of the investigators.

6.2.13 Pharmacokinetic Evaluations

3BNC117-LS and 10-1074-LS serum levels will be measured by validated sandwich ELISA methods performed at Duke University. Serum samples will be collected before 3BNC117-LS and 10-1074-LS administration, at the end of the 3BNC117-LS and 10-1074-LS intravenous infusions and at all follow up visits.

Pharmacokinetic parameters, including AUC, Cmax, T_{1/2}, Tmax, clearance rate and others will be estimated by performing a non-compartmental analysis (NCA). Pharmacokinetic parameters will be examined to correlate exposure with safety and pharmacodynamic parameters (decline in plasma HIV-1 RNA), and variance, based on population intrinsic factors such as weight and gender, will be explored.

6.2.14 Specimen Shipment Preparation, Handling and Storage

- **Safety labs:**

Specimens collected for safety labs at RUH will be transported to Memorial Sloan Kettering Cancer Center laboratory (MSKCC) via a courier. Specimens for LabCorp will be picked up by LabCorp staff at RUH.

Safety labs will be collected and tested at the WCMC and the UPENN sites.

- **Research labs:**

Specimens collected at RUH will be transported to the Clinical Processing lab in the Laboratory of Molecular Immunology by laboratory staff. The buildings are adjacent to each other and are connected by an underground tunnel.

Specimens collected at WCMC will be transported to the Processing Lab on site at the local Clinical Trials Unit.

Specimens collected at UPENN will be transported to the Processing Lab on site at the local Clinical Trials Unit.

1. Peripheral Blood Mononucleated Cells (PBMC) (isolated from ACD tubes or from leukapheresis): PBMCs are isolated using density gradient centrifugation with Histopaque.

PBMC sample aliquots will be stored in liquid nitrogen freezers located at the local sites. PBMCs will also be used for future phenotypic and functional assays to characterize B, T and NK cells, as well future assessments to proviral HIV-1 DNA.

2. Plasma: Samples will be collected from ACD tubes after an initial centrifugation step, prior to PBMC isolation. The collected plasma sample goes through a second centrifugation step and is aliquoted in 1 or 10 ml volumes and stored at -80 degrees Celsius.

Plasma samples will be stored at the local sites. Plasma samples will be used to isolate circulating viral sequences.

3. Serum: Samples will be collected in Serum Separation Tubes (SST). Following centrifugation, serum from multiple tubes, from the same participant, will be pooled, divided in 200 or 500 μ l aliquots and stored at -80 degrees Celsius.

Serum samples will be shipped to the laboratory of Drs. [name] and [name]. Serum samples will be used for measurement of 3BNC117-LS and 10-1074-LS levels, anti-3BNC117-LS and anti-10-107-LS antibodies and for *in vitro* neutralization assays. The remaining aliquots will be stored at the local sites.

All infectious specimens will be transported using packaging mandated in the Code of Federal

Regulations, 42 CFR Part 72. Member carriers such as FedEx will accept or reject packages of dangerous goods on strict adherence to the International Air Transportation Association (IATA) Dangerous Goods Regulations (DGR). Shipments will be compliant with IATA DGR requirements.

6.2.15 Biohazard Containment

As the transmission of HIV-1 and other blood-borne pathogens can occur through contact with contaminated needles, blood, and blood products, appropriate blood and secretion precautions will be employed by all personnel in the drawing of blood and shipping and handling of all specimens for this study, as currently recommended by the Centers for Disease Control and Prevention and the National Institutes of Health.

6.2.16 Compensation

Participants will be compensated according to standards at each study site.

7 INVESTIGATIONAL PRODUCTS

Investigational Drug Name: 10-1074-LS
Manufacturer Name of Drug: Celldex Therapeutics, Inc.
IND Number: 136387
IND Sponsor: Rockefeller University

Investigational Drug Name: 3BNC117-LS
Manufacturer Name of Drug: Celldex Therapeutics, Inc.
IND Number: 131872
IND Sponsor: Rockefeller University

7.1 Regimen

- 3BNC117-LS and 10-1074-LS will be administered intravenously, in sequence, at 30 mg/kg (each mAb) once.

7.2 Study Product Formulation and Preparation

Study Drugs Formulation:

- 3BNC117-LS will be provided by Celldex Therapeutics in single-use vials containing 1 mL of 3BNC117-LS protein at a concentration of 150 mg/mL in a 1.0 mL buffered solution composed of 10 mM Histidine, 245 mM Trehalose, 10 mM Methionine, 0.05% Polysorbate 20, pH 5.2. The drug product is brownish yellow in appearance and slightly opalescent at storage conditions.
- 10-1074-LS will be provided by Celldex Therapeutics in single-use vials containing 1 mL of 10-1074-LS protein at a concentration of 140 mg/mL in buffered solution composed of 5 mM Histidine, 250 mM Trehalose, 10 mM Methionine, 5 mM Sodium Acetate, 0.05% Polysorbate 20, pH 5.5. The drug product is brownish yellow in appearance and slightly opalescent at storage conditions.

Preparation:

- Each mAb will be diluted in normal saline (NaCl 0.9%) to a volume of 100 mL for intravenous infusion. Normal saline will be obtained by the local site pharmacies.
- 3BNC117-LS and 10-1074-LS are stored at $5 \pm 3^{\circ}\text{C}$. The appropriate dose of each mAb should be drawn soon after vials are removed from the refrigerator. Vials should be checked for particulates before drawing doses, but no other swirling or inversion are needed.
- The appropriate dose will be calculated by the site research pharmacist according to participant's weight (measured at the day 0 visit). 3BNC117-LS and 10-1074-LS will be dispensed in a small volume parenteral infusion, diluted in normal saline (NaCl 0.9%) ready for administration by the study investigators. Standard 18G needles are recommended to draw the required dose of each mAb to decrease the preparation time. Prior to injection of the mAb solution into the IV bag, remove air from the syringe and inject slowly, to avoid foaming. After preparation, infusion bags should be handled gently to avoid foaming (do not shake). Infusion bags should also be checked for particulates.

- 3BNC117-LS and 10-1074-LS should be administered through a 0.2 or 0.22 micron in-line filter.
- Finished infusion preparations with IV lines attached and primed may be stored at either room temperature or refrigerated. Infusion beyond use dating depends upon the IV product preparation method and local pharmacy SOPs. A recommendation is to begin the infusion within 4 hours of preparation, if stored at room temperature, and 6 hours, if stored refrigerated (2-8 C).

Dispensing and Handling of Investigational Product:

3BNC117-LS and 10-1074-LS will be shipped from Celldex Therapeutics and will be stored in the site research Pharmacy at $5 \pm 3^{\circ}\text{C}$.

Trial personnel will ensure that the study ID number on the infusion bag matches the study ID assigned to the participant prior to administration.

7.3 Accountability and Disposal of Used and Unused Investigational Product

The date, allocation number and location of storage of the vials will be recorded in a log. During the trial, the product accountability form, and the dispensing log will be monitored. At the end of the trial, unused vials will be returned to Celldex Therapeutics, transferred to the Laboratory of Molecular Immunology at RU for research purposes only, or destroyed.

7.4 Assessment of Participant Adherence with Study Product

Not applicable. Participants will be administered 3BNC117-LS and 10-1074-LS at the study sites on study day 0.

7.5 Concomitant Medications and Procedures

Use of concomitant medications will be reviewed at each study visit. Each participant will have a medication reconciliation record, which will be updated if schedule or dose level changes, and if new medications are initiated.

Participants will be advised and encouraged to initiated ART 12 weeks after 3BNC117-LS and 10-1074-LS infusions. The initiated ART regimen will be recorded.

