Participants will be advised and encouraged to start ART within 4 weeks of receiving 3BNC117-LS and 10-1074-LS infusions or sooner if: VL fails to decrease by $>0.5 \log_{10}$ copies/ml within 2 weeks of antibody infusions, VL increases $> 0.5 \log_{10}$ copies/ml between weekly measurements or significant T-cell decline (confirmed CD4+ T cells < 200 cells/ μ l) is noted. Participants with current CD4 counts > 300 cells/ μ l will be eligible to enroll in the study. Studies with the unmodified 3BNC117 and 10-1074 in the same study population used the same criterion for entry and showed that CD4 counts remained stable during follow up prior to ART initiation (Caskey, Klein et al. 2015, Caskey, Schoofs et al. 2017) (Bar-On et al. 2018). We have maintained the same criterion in this study to facilitate enrollment, given the overall favorable safety profile seen in the previous studies using similar cutoff. To account for the possibility of transient CD4 count fluctuations in participants who have starting CD4 counts of about 300 cells/mm³, we selected 200 cells/mm³ as the cutoff to re-initiate ART sooner than 4 weeks. The selected CD4 count levels might delay initiation of ART by 1 or 2 weeks, compared to using a slightly higher cutoff. It is also unlikely that participants will experience an accelerated decline in CD4 counts in the course of 4 weeks from antibody infusions that would pose significant additional risk of poor outcomes, such as

development of opportunistic infections. However participants will be closely monitored during this period.

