7.9 Required Medications

Not applicable. Participants will be advised and encouraged to initiated ART within 4 weeks after 3BNC117-LS and 10-1074-LS infusions within 4 weeks of receiving 3BNC117-LS and 10-1074-LS infusions, or sooner if: VL fails to decrease by $>0.5 \log_{10}$ copies/ml within 2 weeks of antibody infusions, VL increases $> 0.5 \log_{10}$ copies/ml between weekly measurements or significant T-cell decline (confirmed CD4+ T cell count < 200 cells/ μ l) is noted.

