13 PROCEDURES TO MINIMIZE RISK

- With any new investigational drug, there is a possibility of totally unexpected side effects. On the day of 3BNC117-LS and 10-1074-LS administration, participants will be observed for one hour after administration. The clinical sites are equipped for providing emergency medical interventions in the unlikely event of acute allergic or other reactions. In case of an emergency, after stabilization of the participant, he/she will be transferred to a tertiary care center for specialized medical care.

- Participants will have regularly scheduled visits to the outpatient clinic and routine safety laboratories.
- Participants will be closely monitored for the development of symptoms of ocular disease (such as blurry vision, increased lacrimation, redness, dryness, pain) and the study investigators will perform a directed exam of the eyes. If participants develop symptoms or signs of ocular disease, they will be referred to an ophthalmologist for diagnosis and management. These evaluations will be performed at no cost to the participant.
- HIV-1 RNA levels and CD4+ T cell counts will be monitored during the study. Participants will be advised and encouraged to start ART within 4 weeks of receiving 3BNC117-LS and 10-1074-LS infusions. ART may be initiated sooner if: VL fails to decrease by $>0.5 \log_{10}$ copies/ml within 2 weeks of antibody infusions, VL increases $> 0.5 \log_{10}$ copies/ml between weekly measurements or significant T-cell decline (confirmed CD4+ T cell count < 200 cells/ μ l) is noted. ART will be initiated in collaboration with the participant's HIV primary care physician. ART will not be provided by the study.
- Females of childbearing potential and who participate in sexual activity that might lead to pregnancy will be advised to use two reliable forms of contraception from 10 days prior to and six months after 3BNC117-LS and 10-1074-LS administration. In addition, a pregnancy test will be performed at screening, on the day of mAb administration, and throughout the course of the study. Males who are not anatomically sterile and who participate in sexual activity that might lead to pregnancy will be advised to use condoms from 10 days prior to and six months after 3BNC117-LS and 10-1074-LS administration. Condoms will be provided. Safer sex counseling will be provided for the entire duration of the study.

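### Section 7.5 advises starting ART 12 weeks after infusion, with no early-start triggers, while five other places in the protocol advise it within 4 weeks

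*Combined protocol and SAP*

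**What the plan says.** Section 7.5 (numbered 7.6 in the contents list) covers the review and recording of concomitant medications. Its second paragraph states: "Participants will be advised and encouraged to initiated ART 12 weeks after 3BNC117-LS and 10-1074-LS infusions". It then asks for the regimen to be recorded. It gives no conditions for an earlier start.

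Section 4 states the general rule: "Participants will be advised and encouraged to start ART within 4 weeks of receiving 3BNC117-LS and 10-1074-LS infusions or sooner if" any of three things happens. These are a viral-load fall of no more than 0.5 log10 by week 2, a rise of more than 0.5 log10 between weekly measurements, or a confirmed CD4 count below 200. The synopsis has the same rule and triggers. Section 7.9 says "Participants will be advised and encouraged to initiated ART within 4 weeks after 3BNC117-LS and 10-1074-LS infusions" and repeats the triggers. Section 13, which lists procedures to minimize risk, says "Participants will be advised and encouraged to start ART within 4 weeks of receiving 3BNC117-LS and 10-1074-LS infusions" and gives the same triggers as conditions under which ART may begin sooner. Section 3.7 gives the 4-week limit without triggers and explains its purpose as sustained viral suppression.

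**The concern.** These are instructions to sites on when to advise treatment for viremic people who are off ART, and two different times are given. Staff handling ART have reason to consult 7.5, because that is where the regimen is to be recorded. The nearest correct statement, in 7.9, is a weak backstop: it opens by declaring the section not applicable, and its ART sentence repeats the 4-week phrase.

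At stake is mainly the advice participants receive. Section 3.7 says that two antibodies alone would not be enough as therapy for viremic individuals, and Section 12 warns that resistant virus may be selected. A later start runs against the protocol's own reasoning.

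There is a smaller analytic consequence. Three sites enroll competitively. If they followed different sections, the group in the exploratory rebound outcome (participants who choose to stay off ART beyond week 4) would partly reflect local advice rather than choice.

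**Working it through.** No power or sample-size formula applies, and the documents give no inputs from which 12 weeks could be derived. The check sets every statement of the ART rule side by side.

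| Place | Advised start | Early-start triggers |
|---|---|---|
| Synopsis, Study Design | within 4 weeks | yes |
| Section 3.7 | within 4 weeks | no |
| Section 4 | within 4 weeks | yes |
| Section 7.5 | 12 weeks | no |
| Section 7.9 | within 4 weeks | yes |
| Section 13 | within 4 weeks | yes, worded as permission |

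**Count.** One statement of six says 12 weeks. Five of six say within 4 weeks, and four of six carry triggers.

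**Size of the gap.** 12 − 4 = 8 weeks. This is a minimum, because 4 weeks is an upper limit elsewhere. For a participant advised at week 2 because viral load had not fallen enough, the gap is 12 − 2 = 10 weeks. With 7.5 aligned to the other sections, the gap is zero.

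**Which figure is intended.** Two further pieces of text point to 4 weeks:

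1. Section 4 explains that a CD4 count of 200 was chosen "as the cutoff to re-initiate ART sooner than 4 weeks". It also argues: "It is also unlikely that participants will experience an accelerated decline in CD4 counts in the course of 4 weeks from antibody infusions". Both take week 4 as the reference point.
2. An exploratory outcome (synopsis and Section 3.12) measures the time for viremia to return to baseline in those who choose to stay off ART after week 4. Staying off is therefore the participant's decision, not the advised course.

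The first is reasoning inside a section already counted in the table; the second is separate. The primary viral-load outcome, which runs through week 4, is not used as evidence. A measurement window ending at week 4 fits ART at week 12 equally well.

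**The case against.** The strongest reply is that nobody reading the whole protocol would be misled. Five of six statements agree, including the design section, the risk section and one four headings later in the same chapter. Section 7.5 is mainly about recording medications. It does not forbid earlier ART or cancel triggers stated elsewhere. ART is only advised, is not supplied by the study, and is started with the participant's HIV physician. Viral load is measured at every follow-up visit. Any harm requires a site to rely on 7.5 alone, and how likely that is cannot be judged from the reviewed copy, which lacks Appendix A and the consent form. All of this stands. It limits the consequence but does not remove the contradiction.

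A reader might be tempted to go further in four ways.

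- **That a delay beyond 4 weeks has no safety support.** The forward-looking CD4 argument does stop at 4 weeks. However, Section 4 also says that earlier studies of the parental antibodies "showed that CD4 counts remained stable during follow up prior to ART initiation", with no 4-week limit attached.
- **That the primary antiviral analysis or the sample size is undermined.** The viral-load window is fixed at week 4, and the Section 8.2 figures do not use the ART start time.
- **That pharmacokinetics are certainly affected, or certainly not.** Section 8.2 reports shorter parental half-lives in viremic than in uninfected people (12.8 versus 24 days for 10-1074; 9.6 versus 17.6 days for 3BNC117), and Section 6.2.13 has samples taken at all follow-up visits. An effect of longer viremia is therefore possible, but the documents do not give its size.
- **That the gap can be scaled against Section 4's remark: "The selected CD4 count levels might delay initiation of ART by 1 or 2 weeks".** That remark concerns choosing this CD4 cutoff over a slightly higher one. It is not a benchmark for the general ART rule.

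**Conclusion.** The concern holds as an internal contradiction in an operative instruction. Section 7.5 is the outlier, and 4 weeks is the rule the rest of the protocol is built on. A site following 7.5 alone would advise ART at least 8 weeks later than the other five statements and would depart from a risk-minimization procedure in Section 13.

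The 8-week figure assumes reliance on 7.5 in isolation and compares times of advice, not times at which participants actually start. The point should be corrected because it concerns treatment of viremic participants and the correction is nearly free. It is not a flaw in the design, and no claim is made that pharmacokinetics are unaffected.

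**What to change.** In the Section 7.5 sentence, replace the 12-week timing with within 4 weeks after the infusions, and add: or sooner if the criteria in Section 4 are met. The sponsor should confirm that 4 weeks is intended, notify the three sites, and check that Appendix A and the consent form do not carry the 12-week figure.

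The cost is a one-sentence protocol correction and a clarification letter. Visits, sample size and analysis do not change.
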